16.2.8 Exposure and Infusion Details (Safety Population Cumulative)

Patient ID/ Age/Race/ Ethnicity/ Sex	Disease	Duration of Treatment (Days) Current Study/ Parent Study	Date Performed/ Visit	Start Time/ Stop Time	Infusion Duration	Dose Escalated at this Visit?	Planned Dose (mg/kg)/ Actual Dose Given (mg/kg)	Volume Administered (mL)/ Complete Dose Given?/ % of Expected Dose	Reason Complete Dose Not Given	IRR
xxxxxxxxx/ xx/x/x/x	FSHD	xx/xx	DDMMYYYY Y/Week 1	HH:MM/ HH:MM	HH:MM	Yes/No	x.x/ x.x	xx/ Yes or No/ xx.x%	xxxxxxxxx	Yes/No

Note: FSHD=Facioscapulohumeral muscular dystrophy; LGMD2B=Limb-girdle muscular dystrophy 2B; EO-FSHD=Early Onset Facioscapulohumeral muscular dystrophy

Note: W = white; B = black, African American or of African heritage; P = native Hawaiian or other Pacific islander; A = Asian; I = American Indian or Alaska native; O = Other; H = Hispanic or Latino; N = not Hispanic or Latino; M = male; F = female.

Note: Duration of treatment in current study = (date of last dose - first dose +1)

Note: Duration of treatment in parent study = (date of final dose in parent study - first dose in parent study +1)

Source: Dataset: [NAME], Program: xxxxx.sas, Output: xxxx.rtf, Generated on: DDMMYYYY HH:MM

Page x of y

Programming Note: Sort by disease (EO-FSHD, FSHD or LGMD2B), patient, visit, and start time. IRR = Yes if IRR eCRF has been completed. No, otherwise.

16.2.9 All Adverse Events (Safety Population Cumulative)

EO-FSHD										
Patient ID/ Age/Race/Ethnicity/ Sex	System Organ Class Preferred Term Verbatim Term	Start Date/Time (Day)/ Stop Date/Time (Day)/ Study	Start on Dosing Day? TEAE?	SAE/ Reason ^a	Severity Grade	Out- come ^b	Relation- ship ^c	Ac- tion ^d	Action with Subject ^e	
xxxxxxxxxx/x/x/x/x	xxxxxxxxxxx xxxxxxxxxxx xxxxxxxxxxx	DDMMYYYY/HH:MM (xx)/ DDMMYYYY/HH:MM (xx)/ 003	Yes/ No	Yes/No	Yes/x	xx	xx	xx	xx	xx

Note: FSHD=Facioscapulohumeral muscular dystrophy; LGMD2B=Limb-girdle muscular dystrophy 2B; EO-FSHD=Early Onset Facioscapulohumeral muscular dystrophy

Note: W = white; B = black, African American or of African heritage; P = native Hawaiian or other Pacific islander; A = Asian; I = American Indian or Alaska native; O = Other; H = Hispanic or Latino; N = not Hispanic or Latino; M = male; F = female.

Note: Adverse events coded with MedDRA version 18.1.

- a. Reason for SAE: 1 = Results in death; 2 = Life threatening; 3 = Results in persistent or significant disability/incapacity; 4 = Requires or prolongs hospitalization; 5 = Congenital abnormality/birth defect; 6 = Other medically important event.
- b. Outcome: 1 = Fatal; 2 = Not recovered/not resolved; 3 = Recovered/resolved; 4 = Recovered/resolved with sequelae; 5 = Recovering/resolving; 97 = Unknown.
- c. Relationship: 1 = None; 2 = Unlikely; 3 = Possibly; 4 = Likely; 5 = Definitely.
- d. Action: 0 = None; 1 = Drug withdrawn; 2 = Drug interrupted; 3 = Dose reduced; 4 = Dose increased; 5 = Unknown.
- e. Action with subject: 1 = None; 2 = Medication; 3 = Therapy; 4 = Discontinue from Study; 5 = Other.

Source: Dataset: [NAME], Program: xxxxx.sas, Output: xxx.rtf, Generated on: DDMMYYYY HH:MM

Page x of y

Programming Note: Include all AEs from both parent and current studies. Present Actual Date/Times rather than Derived Date/Time. Sort by disease (EO-FSHD, FSHD or LGMD2B), patient, start date, and preferred term.

16.2.9.1 Adverse Events Occurred on Infusion Day (Safety Population Cumulative)

EO-FSHD

Patient ID/ Age/Race/ Ethnicity/Sex	System Organ Class Preferred Term Verbatim Term	Start Date/Time (Day)/ Stop Date/Time (Day)/ Study	Start on Dosing Day?	Infusion		SAE/ Reason ^a	Severity Grade	Out- come ^b	Relation- ship ^c	Ac- tion ^d	Action with Subject ^e
				Start Time/ Stop Time	TEAE?						
xxxxxxxx/xx/x/x/x	xxxxxxxxxx xxxxxxxxxx xxxxxxxxxx	DDMMYYYY/HH:MM (xx)/ DDMMYYYY/HH:MM (xx)/ 003	Yes	HH:MM/ HH:MM	Yes/No	Yes/x	xx	xx	xx	xx	xx

Note: W = white; B = black, African American or of African heritage; P = native Hawaiian or other Pacific islander; A = Asian; I = American Indian or Alaska native; O = Other; H = Hispanic or Latino; N = not Hispanic or Latino; M = male; F = female.

Note: Adverse events coded with MedDRA v18.1.

- a. Reason for SAE: 1 = Results in death; 2 = Life threatening; 3 = Results in persistent or significant disability/incapacity; 4 = Requires or prolongs hospitalization; 5 = Congenital abnormality/birth defect; 6 = Other medically important event.
- b. Outcome: 1 = Fatal; 2 = Not recovered/not resolved; 3 = Recovered/resolved; 4 = Recovered/resolved with sequelae; 5 = Recovering/resolving; 97 = Unknown.
- c. Relationship: 1 = None; 2 = Unlikely; 3 = Possibly; 4 = Likely; 5 = Definitely.
- d. Action: 0 = None; 1 = Drug withdrawn; 2 = Drug interrupted; 3 = Dose reduced; 4 = Dose increased; 5 = Unknown.
- e. Action with Subject: 1 = None; 2 = Medication; 3 = Therapy; 4 = Discontinue from Study; 5 = Other.

Source: Dataset: [NAME], Program: xxxxx.sas, Output: xxxx.rtf, Generated on: DDMMYYYY HH:MM

Page x of y

16.2.9.2 Infusion-Related Reaction Symptoms (Safety Population Cumulative)

EO-FSHD

Patient ID/ Age/Race/Ethnicity/Sex	Infusion-Related Reaction AE Date	Signs/Symptoms	Start Date/Time/ End Date/Time/ Parent Study	Infusion Start Time/Stop Time	Intensity Grade	Outcome ^a
xxxxxxx/xx/x/x/x	DDMMYYYY	xxxxxxxxxxxxxx	DDMMYYYY/HH:MM/ DDMMYYYY/HH:MM/ 003	HH:MM/HH:MM	xx	xx

Note: W = white; B = black, African American or of African heritage; P = native Hawaiian or other Pacific islander; A = Asian; I = American Indian or Alaska native; O = Other; H = Hispanic or Latino; N = not Hispanic or Latino; M = male; F = female.

Note: Adverse events coded with MedDRA v18.1.

a. Outcome: 1 = Fatal; 2 = Not recovered/not resolved; 3 = Recovered/resolved; 4 = Recovered/resolved with sequelae; 5 = Recovering/resolving; 97 = Unknown.

Source: Dataset: [NAME], Program: xxxxx.sas, Output: xxxx.rtf, Generated on: DDMMYYYY HH:MM

Page x of y

16.2.10 Laboratory Data (Safety Population Cumulative)

EO-FSHD

Patient ID/ Age/Race/Ethnicity/Sex	Category	Laboratory Parameter (unit)	Visit	Sample Date	Result	Change from Baseline	Normal Range	Flag
xxxxxxxxxx/x/x/x	xxxxxxxxxxxxx	xxxxxxxxxxxxx	xxxxxxx xxxxxxx	DDMMYYYY DDMMYYYY	xxx.xx xxx.xx	xx.xx	xxx.xx – xxx.xx xxx.xx – xxx.xx	High High

Note: FSHD=Facioscapulohumeral muscular dystrophy; LGMD2B=Limb-girdle muscular dystrophy 2B; EO-FSHD=Early Onset Facioscapulohumeral muscular dystrophy
 Note: W = white; B = black, African American or of African heritage; P = native Hawaiian or other Pacific islander; A = Asian; I = American Indian or Alaska native; O = Other; H = Hispanic or Latino; N = not Hispanic or Latino; M = male; F = female.
 Source: Dataset: [NAME], Program: xxxxx.sas, Output: xxx.rtf, Generated on: DDMMYYYY HH:MM
 Page x of y

Programming Note: Include all lab data, complement, tryptase, screening serology, and pregnancy data in this listing. Category = Hematology, Serum Chemistry, Urinalysis, Complement, Tryptase, Serology, Pregnancy results. Sort by disease (EO-FSHD, FSHD or LGMD2B), patient, visit, sample date, category (hematology, serum chemistry, urinalysis, complement, tryptase, serology, and pregnancy results), and lab parameter (same order as protocol).

Sponsor: aTyr Pharma, Inc.
 Protocol No: ATYR1940-C-006

Statistical Analysis Plan
 Effective Date: 19-Jul-2017/Version 2.0

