- 15 Clinical safety laboratory tests include clinical chemistry, hematology, and urine analysis with microscopy. On the designated dosing days, blood samples for safety laboratory tests are to be collected pre-infusion. Patients with evidence of a generalized IRR are to have additional safety laboratory tests performed, as described in Section 8.5.9.4.
- 16 Blood samples for complement factors in plasma (including C3a, C4a, C5a, Bb, and SC5b-9) will be collected on the designated dosing days prior to and 1.5 hours (± 15 minutes) after the end of infusion and at the designated follow-up visit. In addition, samples for complement factors in plasma are to be collected in the event of a generalized IRR (see Section 8.5.9.4).

- 17 Blood samples for tryptase, C3, C4, and CH50 will be collected on the designated dosing days prior to and 1.5 hours (± 15 minutes) after the end of infusion on the designated dosing days and at the designated follow-up visit. In addition, samples for assessment of tryptase, C3, C4, and CH50 are to be collected in the event of a generalized IRR (see Section 8.5.9.4).
- 18 Blood samples for assessment of Jo-1 Ab are to be collected on dosing days prior to initiation of infusion, and at the additional time points indicated. The Week 1 Jo-1 Ab sample must be obtained and result reviewed within 2 weeks prior to the first ATYR1940 dose. In addition, samples for assessment of Jo-1 Ab are to be collected in the event of a generalized IRR (see Section 8.5.9.4).
- 19 Blood samples for analysis of antidrug antibodies (ADA) are to be collected on the designated dosing days prior to initiation of infusion and at the additional time points indicated. Blood samples for assessment of ADA are to be collected in the event of a generalized IRR (see Section 8.5.9.4). For patients with elevated ADA at the 12-week F/U visit, additional ADA testing should be performed every 1 to 3 months until level returns to baseline.
- 20 Blood samples for assessment of ATYR1940 concentrations are to be collected on the designated dosing days at end of infusion and 4 hours after the start of infusion. ATYR1940 serum concentrations also are to be collected in the event of a generalized IRR (see Section 8.5.9.4).

LIST OF ABBREVIATIONS

Abbreviation	Definition
Ab	Antibody
ADA	Anti-drug antibody
AE	Adverse event
ALT	Alanine aminotransferase
AST	Aspartate aminotransferase
CA	Competent Authority
CK	Creatine kinase
C _{max}	Maximum serum concentration

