8.5.9.3. Antibody and HARS Measurements

Blood samples for measurement of Jo-1 Ab, ADA, and serum HARS levels are to be collected according to the schedule defined in [Table 1](#). Samples will be analyzed by a central laboratory. The Week 1 Jo-1 Ab sample must be obtained and result reviewed within 2 weeks prior to the first ATYR1940 dose.

For patients with elevated ADA at the 12-week F/U visit, additional ADA testing should be performed every 1 to 3 months until the level returns to the pre-infusion baseline.

8.5.9.4. Additional Laboratory Testing and Procedures in Patients with Generalized Infusion-Related Reactions

Patients who experience generalized IRRs (see Section [7.5.5.1](#)) must have their infusion stopped and be treated as medically indicated. Vital signs, pulse oximetry, and ECGs are to be performed to gather clinical information as soon as possible after the onset of clinical symptoms of a generalized IRR (for instance, immediately after cessation of the study drug infusion if such a reaction is seen). Vital signs are to be monitored as medically indicated and pulse oximetry is to be monitored continuously for at least 2 hours after the end of infusion or until the patient has recovered, whichever is longer. ECGs should be repeated as medically indicated.

Once medical treatment of the IRR has begun, blood samples are to be obtained for assessment of:

- Plasma complement factors (C3a, C4a, C5a, Bb, and SC5b-9)
- Serum complement (CH50, C3, and C4) and trypsin

Additionally, the following tests and procedures are to be performed 1.5 to 2 hours after the onset of symptoms:

- Samples for assessment of:
 - Complete safety laboratory panel, including urine analysis and microscopy ([Section 8.5.9.1](#))
 - Plasma complement factors (C3a, C4a, C5a, Bb, and SC5b-9)
 - Serum complement (CH50, C3, and C4) and trypsin
 - Biomarkers and ATYR concentrations
- PFTs – FEV₁, FVC, FEV₁/FVC ratio, total lung capacity, DLCO

The Investigator must inform the study Medical Monitor promptly regarding any patient who experiences a generalized IRR for additional instruction.

Patients who experience generalized IRRs will continue to be monitored / have repeat assessments performed at a schedule determined by the Investigator in consultation with the Medical Monitor and Sponsor. Appropriate follow up for the patient must occur to ensure that there are no late-occurring sequelae.

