9. STATISTICAL ANALYSES

9.1. Statistical Basis for Sample Size

No formal sample size calculation was performed; patients that participated in the parent study and meet the entry criteria for the current study may be enrolled. Based on the design of the parent studies, it is estimated that up to 24 patients will be enrolled in this study.

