9.2.8. Safety Analysis

9.2.9. Safety and Immunogenicity Analyses

Safety evaluations will be based on the incidence, type, and intensity of AEs, and changes from baseline in safety laboratory tests, ECG findings, vital signs measurements, PFTs, and pulse oximetry. Immunogenicity will be assessed based on the incidence of infusion site reactions, ADA titers, changes in Jo-1 and ADA titers over time, as appropriate, as well as changes from baseline over time in immune-based laboratory tests, including, for example, tryptase, complement factors, and cytokines. Safety variables will be tabulated and presented for all patients who receive any amount of study drug and have follow-up safety data. Tabulations will be presented for safety data overall and separately for the parent and extension studies.

AEs will be coded using the current version of the Medical Dictionary for Regulatory Activities (MedDRA) for purposes of summarization. The overall incidence of AEs occurring during the study will be summarized by MedDRA system organ class and preferred term. The incidence of TEAEs also will be summarized by system organ class

and preferred term. For the purpose of analysis, a TEAE is defined as any AE that occurs after administration of the first dose of ATYR1940 through the 12-week posttreatment follow-up visit, or any event that is present at baseline, but worsens in intensity or is subsequently considered drug-related by the Investigator. Severe TEAEs, SAEs, and discontinuation rates of study therapy due to TEAEs also will be summarized.

Events that are considered related to treatment (possibly, likely, or definitely drug-related) will also be tabulated. A tabulation will also be provided that enumerates TEAEs by maximum severity. Deaths, SAEs, and TEAEs resulting in study discontinuation will be tabulated, if warranted by the data.

All AEs occurring on study will be listed in by-patient data listings.

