12. Upper extremity function to be measured using the Brooke scale; lower extremity function to be measured using the Vignos scale.
13. The FSHD HI should be completed at the same time of day and before other assessments scheduled for that day, including the InQoL. The order of assessments should remain consistent throughout the study.
14. Urine pregnancy testing is required for females of childbearing potential (i.e., premenopausal and not surgically sterile) only. Pregnancy testing must be performed within 7 days before ATYR1940 administration at ESW1. Testing is to be performed using the local laboratory and before study drug infusion.
15. Clinical safety laboratory tests include clinical chemistry, hematology, and urine analysis with microscopy. On the designated dosing days, blood samples for safety laboratory tests are to be collected pre-infusion. Patients with evidence of a generalized IRR are to have additional safety laboratory tests performed, as described in Section 8.5.9.4 of the protocol.
16. Blood samples for complement factors in plasma (including C3a, C4a, C5a, Bb, and SC5b-9) will be collected on the designated dosing days prior to and 1.5 hours (± 15 minutes) after the end of infusion and at the designated follow-up visit. In addition, samples for complement factors in plasma are to be collected in the event of a generalized IRR (see Section 8.5.9.4 of the protocol).
17. Blood samples for tryptase, C3, C4, and CH50 will be collected on the designated dosing days prior to and 1.5 hours (± 15 minutes) after the end of infusion on the designated dosing days and at the designated follow-up visit. In addition, samples for assessment of tryptase, C3, C4, and CH50 are to be collected in the event of a generalized IRR (see Section 8.5.9.4 of the protocol).

18. Blood samples for assessment of Jo-1 Ab are to be collected on dosing days prior to initiation of infusion, and at the additional time points indicated. The Week 1 Jo-1 Ab sample must be obtained and result reviewed within 2 weeks prior to the first ATYR1940 dose. In addition, samples for assessment of Jo-1 Ab are to be collected in the event of a generalized IRR (see Section 8.5.9.4 of the protocol).

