4.0 Study Endpoints and Covariates

4.1 Safety, Tolerability, and Immunogenicity Variables

4.1.1 Safety and Tolerability

The safety and tolerability of ATYR1940 will be evaluated based on the following variables:

- Treatment-emergent adverse events (AEs)
- Serious adverse events (SAEs)
- Clinical laboratory tests:
 - Hematology, serum chemistry, and urinalysis
 - Complement and tryptase
- Electrocardiogram (ECG) results
- Vital signs
- Physical and neurological examinations
- Pulmonary evaluations
 - Pulmonary function tests (PFTs)
 - Forced expiratory volume in 1 second (FEV₁)
 - Forced vital capacity (FVC)
 - FEV₁/FVC ratio
 - Total lung capacity
 - Diffusion capacity of carbon monoxide (DLCO)
 - Pulse oximetry
 - Oxygen saturation (SpO₂) measurements
 - SpO₂ measurements below 95%

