9.0 Overall Statistical Considerations

All analyses will use SAS® version 9.4 or higher. Summary tables will be organized overall and by disease group, if applicable, for the two Safety populations. All available data will be used in the analyses, and important data will be included in data listings, sorted by site, patient and by visit within patient.

Unless otherwise noted, categorical data will be presented using counts and percentages, with the number of patients in the corresponding Safety population as the denominator for percentages. Percentages will be rounded to one decimal place except 100% will be displayed without any decimal places and percentages will not be displayed for zero counts. Continuous data, unless otherwise noted, are summarized using the number of observations (n), mean, standard deviation (SD), median, minimum, and maximum. Minimum and maximum will be rounded to the precision of the original value. Mean and median will be rounded to 1 decimal place greater than the precision of the original value. The SD will be rounded to 2 decimal places greater than the precision of the original value, up to a maximum of 3 decimal places. No statistical hypothesis testing will be performed for this study.

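### The protocol's change-from-baseline analysis of complement and tryptase has no SAP summary, and their only listing cannot separate pre-infusion, post-infusion and reaction-triggered results

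*SAP*

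**What the plan says.** **Collection.** Notes 16 and 17 of the Schedule of Events (Table 1 in both the protocol and SAP 3.1) require paired samples. For plasma: "Blood samples for complement factors in plasma (including C3a, C4a, C5a, Bb, and SC5b-9) will be collected on the designated dosing days prior to" infusion and again 1.5 hours after it ends. For serum: "Blood samples for tryptase, C3, C4, and CH50 will be collected on the designated dosing days prior to and 1.5 hours" after the end of infusion. The schedule places these draws at the 12-weekly visits, with a further sample at the 1-week follow-up. For a generalized IRR, Protocol 8.5.9.4 adds two sets of the same analytes. The first is introduced by "Once medical treatment of the IRR has begun, blood samples are to be obtained for assessment of"; the second is due 1.5 to 2 hours after symptom onset.

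**Planned analysis.** Protocol 9.2.9 lists, among the bases for judging immunogenicity, "changes from baseline over time in immune-based laboratory tests, including, for example, tryptase, complement factors, and cytokines". SAP 4.1.1 includes "Complement and tryptase" among the clinical laboratory tests used to evaluate safety.

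**Planned output.** Listing 16.2.10 carries the instruction "Include all lab data, complement, tryptase, screening serology, and pregnancy data in this listing". Its columns are patient, category, parameter, visit, sample date, result, change from baseline, normal range and flag. Rows are sorted by disease, patient, visit, sample date, category and parameter.

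**The concern.** The protocol commits to an analysis, the SAP accepts the variables, and the output then stops at a listing that cannot show which sample is which. Generalized IRR is an identified risk of this product: Protocol 7.5.5.1 reports three patients, with one event considered serious. Safety and immunogenicity are the first study objective. Complement and tryptase are among the laboratory measures taken around the infusion.

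If the SAP is followed as written, the study report will contain no summary of their change over time. A reader of the listing will see two results for one analyte on one date without knowing which came before the drug. The change-from-baseline value printed beside each result has the same defect, because it may compare baseline with a resting level or with a level just after infusion.

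**Working it through.** There is no stated figure to reproduce. The study is descriptive ("No statistical hypothesis testing will be performed for this study"), so no alpha, power or effect size bears on the point. The check sets the sections side by side and then counts rows.

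**1. Is there a summary anywhere?**
- SAP 9.6.2 summarises hematology, serum chemistry and urinalysis. Its Table 2 contains no complement factor and no tryptase.
- SAP 9.6.7 tabulates maximum ADA titer and Jo-1 antibody level only.
- The table index in Appendix 4 has no complement or tryptase table under 14.2.2 (laboratory) or 14.2.6 (immunogenicity).
- The PK/PD SAP (sections 4.1 and 7) covers ATYR1940, HARS, cytokines, PBMC immunophenotyping and a comparison of ATYR1940 concentrations in ADA-positive patients. Of the three examples named in Protocol 9.2.9, cytokines therefore have an output; tryptase and complement do not.
- SAP 1.1 mentions complement and tryptase only to waive the repeat Week 1 draw. It does not record the missing summary as a change.

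**2. Can the listing stand in for a summary?**

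| Listing | Time point or sample time | IRR flag | Change from pre-infusion |
|---|---|---|---|
| ECG part 2 (16.2.12) | Time point | Yes | Yes |
| Vital signs (16.2.13) | Time point | Yes | Yes |
| ADA (16.2.17.1) | Sample date/time | Yes | No |
| Jo-1 (16.2.17.2) | Sample date/time | Yes | No |
| Laboratory data (16.2.10) | Neither | No | No |

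The sort keys of 16.2.10 end at the parameter, so the order of rows within a same-day pair is also undefined.

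**3. How many rows are affected?**
- Analytes: 5 in plasma (C3a, C4a, C5a, Bb, SC5b-9) + 4 in serum (tryptase, C3, C4, CH50) = 9.
- Rows per patient per 12-weekly visit: 9 × 2 = 18, forming 9 pairs.
- Enrolment: the protocol states that "it is estimated that up to 24 patients will be enrolled in this study". The maximum per visit is 18 × 24 = 432 rows, or 9 × 24 = 216 pairs.
- If an IRR falls on such a visit, the two extra sets add 2 × 9 = 18 rows. That patient then has 9 + 18 = 27 rows if the routine post-infusion sample is not taken, or 18 + 18 = 36 if it is.

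**4. Is the baseline itself secure?** SAP 6.0 uses the parent-study baseline throughout and calculates no change when a baseline was not recorded. SAP 1.1 confirms complement and tryptase draws at parent Week 14. Neither document confirms a draw before the first parent dose. If none exists, the change-from-baseline column would be empty for these analytes.

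**The case against.** The strongest reply has four parts.

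*The protocol promises change from baseline, not pre-to-post change.* This is correct. A reader might infer from the paired sampling that a pre-to-post analysis was planned, but Protocol 9.2.9 does not say so, and SAP 6.0 confines that comparison to vital signs and ECG. The shortfall against the protocol is the missing and undeclared change-from-baseline summary. The pre-to-post comparison is a sensible addition that uses samples already drawn. The listing defect still affects the promised analysis, because a change from baseline on a dosing day is ambiguous without a time point.

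*A shell governs display, not retention.* This also stands. A reader might conclude that the pairing is thrown away, but nothing says time points are dropped from the datasets described in SAP 8.3. The Visit cell is a placeholder, and Tables 14.2.3.1 and 14.2.4.1 do carry the time point in the visit label. However, the ECG and vital-sign listings use a separate column and the laboratory shell gives no instruction either way. The single-sample 1-week follow-up remains readable.

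*The importance of the routine pairs can be overstated.* A reader might take them as the evidence on how infusion reactions arise. The documents make no such claim. A generalized IRR ends dosing under Protocol 6.4.1, so routine pairs mostly describe infusions without a reaction. The reaction-related samples are the separate IRR sets. SAP 9.6.2 has additional IRR safety laboratory data listed and not summarised, which makes the absence of an IRR flag in this listing more awkward.

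*Protocol 9.2.9 allows further safety analyses at any time.* That permission does not supply an analysis the same section already specifies.

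**Conclusion.** The point holds in this form. A protocol-specified component of the immunogenicity assessment has no summary in either analysis plan, the omission is not declared, and the only listing cannot distinguish same-day samples. The size is all nine analytes at every 12-weekly dosing visit: up to 216 unlabelled pairs per visit, assuming 24 patients are enrolled, all are still attending and every scheduled sample is drawn. Fewer patients or missed samples reduce the count in proportion.

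The conclusion rests on the shells being programmed as shown. It does not depend on data being lost or on any particular view of how infusion reactions occur. It should be settled before database lock because it concerns delivery of a planned safety analysis. It does not put the study's conduct or its other safety outputs in doubt.

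**What to change.** 1. **Listing 16.2.10:** add a Time Point (or Sample Date/Time) column and an IRR column, as in the ECG, vital-sign, ADA and Jo-1 listings, and add time point to the sort keys.
2. **New table modelled on 14.2.3.1**, by visit and disease group, for the nine analytes. Show the actual value, change from baseline using scheduled pre-infusion samples only, and change from pre-infusion to 1.5 hours after infusion. Keep IRR samples in the listing only.
3. **Baseline:** use the parent-study baseline if it was collected; otherwise use the earliest available pre-infusion sample. State the choice in a footnote, and say there if that sample was taken after treatment had begun.
4. **SAP 6.0:** extend the pre-to-post-infusion definition to complement and tryptase.

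If the sponsor prefers not to add the table, SAP 1.1 should declare and justify the omission; the listing columns are still needed.

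The cost is two listing columns and one reused shell, run for nine analytes across three disease groups and the total, with two time points per dosing visit. That is modest extra programming, with no new sampling and no change to patient management. The SAP's document history describes Version 2.0 as a draft updated after the dry run, so the edit fits the process already under way.
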